## 2. ABBREVIATIONS

Abbreviations pertain to the Statistical Analysis Plan (SAP) only (not the tables, figures and listings [TFLs]).

ADA	Antidrug antibody
AE	Adverse event
AUC	Area under the concentration versus time curve
AUC(0-∞)	Area under the concentration versus time curve from zero to infinity
BMI	Body Mass Index
C max	Maximum observed drug concentration
CI	Confidence Interval
CRF	Case Report Form
CSR	Clinical Study Report
CRU	Clinical Research Unit
CV	Coefficient of variation
EC	Early Clinical
ECG	Electrocardiogram
e.g.	For example (Latin: exempli gratia )
FU	Follow Up
ICH	International Conference on Harmonisation
IV	Intravenous
MedDRA	Medical Dictionary for Regulatory Activities
PK	Pharmacokinetic
SAP	Statistical Analysis Plan
SC	Subcutaneous
SD	Standard deviation
TFLs	Tables, Figures, and Listings
WHO	World Health Organization

### **3. INTRODUCTION**

This SAP has been developed after review of the Clinical Study Protocol (final version dated 11 August 2015), and Amendment (a) (final version dated 23 January 2018).

This SAP describes the planned analysis of the safety, tolerability and pharmacokinetic (PK) data from this study. A detailed description of the planned TFLs to be presented in the clinical study report (CSR) is provided in the accompanying TFL shell document.

The intent of this document is to provide guidance for the statistical and PK analyses of data. In general, the analyses are based on information from the protocol, unless they have been modified by agreement between Eli Lilly and Company and Covance Early Clinical (EC) Biometrics. A limited amount of information concerning this study (e.g., objectives, study design) is given to help the reader's interpretation. This SAP must be signed off prior to first subject administration for this study. When the SAP and TFL shells are agreed upon and finalized, they will serve as the template for this study's CSR.

This SAP supersedes the statistical considerations identified in the protocol; where considerations are substantially different, they will be so identified. If additional analyses are required to supplement the planned analyses described in this SAP, they may be performed and will be identified in the CSR. Any substantial deviations from this SAP will be agreed upon between Eli Lilly and Company and Covance EC Biometrics and identified in the CSR. Any minor deviations from the TFLs may not be documented in the CSR.

This SAP is written with consideration of the recommendations outlined in the International Conference on Harmonisation (ICH) E9 Guideline entitled Guidance for Industry: Statistical Principles for Clinical Trials and the ICH E3 Guideline entitled Guidance for Industry: Structure and Content of Clinical Study Reports.

### **4. STUDY OBJECTIVES**

#### **Primary Objective**

The primary objective is to explore the safety and tolerability of LY3074828 in healthy Japanese and Caucasian subjects to define an appropriate dose for further clinical research in Japan.

#### **Secondary Objectives**

[figure not shown]
The secondary objectives of this study are

- to estimate the PK parameters of LY3074828 following intravenous (IV) and subcutaneous (SC) administration in healthy Japanese and Caucasian subjects.
- to explore the safety, tolerability, and PK of LY3074828 in Japanese subjects in relation to Caucasian subjects.

## 5. STUDY DESIGN

This is a single-site, subject- and investigator-blind, randomized, placebo-controlled, single-dose study to assess the safety, tolerability, and PK of LY3074828 in Japanese and Caucasian healthy subjects. Subjects will be randomized to LY3074828 or placebo within 1 of 6 cohorts, as shown in Figure 1. Cohort 1 will consist of 10 subjects (6 Japanese and 4 Caucasian) who will be randomized so that 5 Japanese subjects and 3 Caucasian subjects will receive LY3074828 while 1 Japanese subject and 1 Caucasian subject will receive placebo. Cohorts 2 through 6 will consist of 8 subjects (4 Japanese and 4 Caucasian) who are randomized in a 3:1 ratio of LY3074828 to placebo. For each cohort, 3 Japanese subjects and 3 Caucasian subjects will receive LY3074828 while 1 Japanese subject and 1 Caucasian subject will receive placebo.

Single doses up to 600 mg IV have been studied and shown to be well tolerated, therefore all cohorts, with the exception of Cohort 5 and Cohort 6, may be dosed in parallel if the site is able to accommodate more than 1 cohort at a time. Cohort 5 will be dosed after confirming the safety and PK data from Cohort 1. Cohort 6 will be dosed last after confirming the safety and PK data from Cohort 5. Two additional Japanese subjects will be included in Cohort 1 to ensure that a sufficient number of Japanese subjects will have received LY3074828 at the time of the interim analysis. An interim analysis is planned based on Cohort 1 data through Day 15 to support Japanese patients being included in the planned global Phase 2 study, Study I6T-MC-AMAC (AMAC).

Abbreviations: FU = follow up; IV = intravenous; SC = subcutaneous

**Figure. 1 Study design**

## **Treatment**

Five IV dose levels and 1 SC dose level of LY3074828 will be assessed in Cohorts 1 through 6. The following treatments are planned:

Cohort 1: a single dose of LY3074828 600 mg or placebo IV  
Cohort 2: a single dose of LY3074828 200 mg or placebo IV  
Cohort 3: a single dose of LY3074828 200 mg or placebo SC  
Cohort 4: a single dose of LY3074828 60 mg or placebo IV  
Cohort 5: a single dose of LY3074828 1200 mg or placebo IV  
Cohort 6: a single dose of LY3074828 2400 mg or placebo IV

## **6. TREATMENTS**

The following is a list of the study treatment abbreviations that will be used in the TFLs.

Study Treatment Name	Treatment order in TFL
Placebo SC	1
Placebo IV	2
Pooled Placebo	3
60 mg LY3074828 IV	4
200 mg LY3074828 SC	5
200 mg LY3074828 IV	6
600 mg LY3074828 IV	7
1200 mg LY3074828 IV	8
2400 mg LY3074828 IV	9
Pooled LY3074828	10

## **7. SAMPLE SIZE JUSTIFICATION**

Up to 60 subjects may be enrolled in order that approximately 50 subjects complete the study. It is intended that 10 subjects (6 Japanese and 4 Caucasian) will be randomized in Cohort 1, and 8 subjects (4 Japanese and 4 Caucasian) will be randomized in Cohorts 2, 3, 4, 5, and 6. The sample size is customary for Phase 1 studies evaluating safety, tolerability, and PK parameters.

Subjects who are randomized but not administered treatment or do not provide sufficient safety and/or PK data may be replaced if judged necessary by the Lilly clinical pharmacologist. The replacement subject should be assigned to the same treatment as the discontinued subject and should be Japanese or Caucasian to match the discontinued subject.

## **8. DEFINITION OF ANALYSIS POPULATIONS**

The “Safety” population will consist of all enrolled subjects, whether or not they completed all protocol requirements.

The “Pharmacokinetic” population will consist of all data from all randomized subjects receiving at least one dose of the study drug according to the treatment the subjects actually received.

All protocol deviations that occur during the study will be considered for their severity/impact and will be taken into consideration when subjects are assigned to analysis populations.

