blinding	a procedure in which one or more parties to the trial are kept unaware of the treatment assignment(s). Unless otherwise specified, blinding will remain in effect until final database lock. A single-blind study is one in which the investigator and/or his staff are aware of the treatment but the subject is not, or vice versa, or when the sponsor is aware of the treatment but the investigator and his staff and the subject are not. A double-blind study is one in which neither the subject nor any of the investigator or sponsor staff who are involved in the treatment or clinical evaluation of the subjects are aware of the treatment received.
CD	Crohn's disease
CI	confidence interval
CIOMS	Council for International Organizations of Medical Sciences
C_{max}	maximum drug concentration
complaint	a complaint is any written, electronic, or oral communication that alleges deficiencies related to the identity, quality, purity, durability, reliability, safety or effectiveness, or performance of a drug or drug delivery system.
compliance	adherence to all the trial-related requirements, good clinical practice (GCP) requirements, and the applicable regulatory requirements.
confirmation	a process used to confirm that laboratory test results meet the quality requirements defined by the laboratory generating the data and that Lilly is confident that results are accurate. Confirmation will either occur immediately after initial testing or will require that samples be held to be retested at some defined time point, depending on the steps required to obtain confirmed results.
CRF	case report form/electronic case report form: sometimes referred to as clinical report form; a printed or electronic form for recording study participants' data during a clinical study, as required by the protocol.

CRU	clinical research unit
CSE	clinically significant event: a moderate to severe adverse event (AE), abnormal clinical sign, or clinical laboratory finding that may pose a risk to the well-being of the subject
CTCAE	Common Terminology Criteria for Adverse Events
end of study	End of study is the date of the last visit or last scheduled procedure shown in the Study Schedule for the last patient/subject.
enroll	the act of assigning a subject to a treatment. Subjects who are enrolled in the trial are those who have been assigned to a treatment.
enter	Subjects entered into a trial are those who sign the informed consent form directly or through their legally acceptable representatives.

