8.2.1. Discontinuation of Subjects

8.2.1.1. Subjects Inadvertently Enrolled

The criteria for enrollment must be followed explicitly. If the investigator site identifies a subject who did not meet enrollment criteria and who was inadvertently enrolled, the sponsor must be notified. If the sponsor identifies a subject who did not meet enrollment criteria and who was inadvertently enrolled, the investigator site will be notified. A discussion must occur between the Lilly clinical pharmacologist or clinical research physician and the investigator to determine whether the subject may continue in the study without IP. The subject may not continue in the study if the Lilly clinical pharmacologist or clinical research physician does not agree with the investigator's determination it is medically appropriate for the subject to continue. The investigator must obtain documented approval from Lilly clinical pharmacologist or clinical research physician to allow the inadvertently enrolled subject to continue in the study.

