11.2. Data Analysis Plans

11.2.1. General Considerations

Statistical analysis of this study will be the responsibility of Eli Lilly and Company or its designee.

PK analyses will be conducted on the full analysis set. This set includes all data from all randomized subjects receiving at least one dose of the IP according to the treatment the subjects actually received. Safety analyses will be conducted for all enrolled subjects, whether or not they completed all protocol requirements.

Additional exploratory analyses of the data will be conducted as deemed appropriate. Analyses will be fully detailed in the statistical analysis plan. Study results may be pooled with the results of other studies for population PK analysis purposes to avoid issues with post-hoc analyses and incomplete disclosures of analyses.

Data from subjects receiving placebo in the IV cohorts will be pooled to form 1 placebo group.

Data will be also summarized by race (Japanese and Caucasian) where appropriate.

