## **9. STATISTICAL METHODOLOGY**

### **9.1 General**

Data listings will be provided for all data that is databased. Summary statistics and statistical analysis will only be presented for data where detailed in this SAP. For continuous data, summary statistics will include the arithmetic mean, arithmetic standard deviation (SD), median, min, max and N; for log-normal data (e.g. the PK parameters: area under the concentration versus time curve [AUCs] and maximum observed drug concentration [ $C_{max}$ ]) the geometric mean and geometric coefficient of variation (CV%) will also be presented. For categorical data, frequency count and percentages will be presented. Data listings will be provided for all subjects up to the point of withdrawal, with any subjects excluded from the relevant population highlighted. Summary statistics and statistical analyses will generally only be performed for subjects included in the relevant analysis population. For the calculation of summary statistics and statistical analysis, unrounded data will be used.

Mean change from baseline is the mean of all individual subjects' change from baseline values. Each individual change from baseline will be calculated by subtracting the individual subject's baseline value from the value at the timepoint. The individual subject's change from baseline values will be used to calculate the mean change from baseline using a SAS procedure such as Proc Univariate.

Data from subjects receiving placebo in the IV cohorts will be pooled to form 1 placebo group. Data will be also summarized by population (overall, Japanese and Caucasian) where appropriate. The clinical chemistry and hematology, vital signs, and electrocardiogram (ECG) data will only be summarized by population if a trend is observed.

Data analysis will be performed using SAS® Version 9.4.

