## **9.4 Safety and Tolerability Assessments**

### **9.4.1 Adverse events**

Where changes in severity are recorded in the Case Report Form (CRF), each separate severity of the adverse event (AE) will be reported in the listings, only the most severe will be used in the summary tables. A pre-existing condition is defined as an AE that starts before the subject has provided written informed consent and is ongoing at consent. A non-treatment emergent AE is defined as an AE which starts after informed consent but prior to dosing. A treatment-emergent AE is defined as an AE which occurs postdose or which is present prior to dosing and becomes more severe postdose.

All AEs will be listed. Treatment-emergent AEs will be summarized by population, treatment, severity and relationship to the study drug. The frequency (the number of AEs, the number of subjects experiencing an AE and the percentage of subjects experiencing an AE) of treatment-emergent AEs will be summarized by population, treatment, Medical Dictionary for Regulatory Activities (MedDRA) version 18.0 system organ class and preferred term. The summary and frequency AE tables will be presented for all causalities and those considered related to the study drug. Any serious AEs will be tabulated.

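### The Safety population has no dosing condition, so a subject who is randomized but never dosed could count in the denominator of the TEAE percentages

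*SAP*

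**What the plan says.** SAP section 8 states that the Safety "population will consist of all enrolled subjects, whether or not they completed all protocol requirements". Protocol section 11.2.1 agrees: "Safety analyses will be conducted for all enrolled subjects, whether or not they completed all protocol requirements". The SAP does not define enrolment, so the protocol's definition in section 4 applies: "Subjects who are enrolled in the trial are those who have been assigned to a treatment". Neither document adds a dosing condition for safety. The Pharmacokinetic population, defined next in SAP section 8, does require at least one dose and goes by the treatment actually given.

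The documents foresee undosed subjects in two places. SAP section 7 (and protocol section 11.1) says: "Subjects who are randomized but not administered treatment or do not provide sufficient safety and/or PK data may be replaced if judged necessary". Protocol section 8.2.1.1, on subjects enrolled in error, calls for a discussion "to determine whether the subject may continue in the study without IP".

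On the analysis, SAP section 9.4.1 states: "A treatment-emergent AE is defined as an AE which occurs postdose or which is present prior to dosing and becomes more severe postdose". The same section reports the number of events and the number and percentage of subjects affected, by population (overall, Japanese, Caucasian) and treatment. It names no denominator. SAP section 9.1 gives the general rule: "Summary statistics and statistical analyses will generally only be performed for subjects included in the relevant analysis population".

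**The concern.** A TEAE needs a postdose period. A subject who was never dosed cannot enter the numerator of a TEAE percentage, but is a member of the population on which safety summaries are generally made. If the tables follow SAP section 9.1, that subject adds one to the denominator and nothing to the numerator, and the percentage in that column is too low.

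Safety and tolerability is the primary objective, and Japanese subjects in relation to Caucasian subjects is a secondary one. The columns are small, so a single subject can move a percentage visibly. The direction is also the unhelpful one for a safety summary, since events look less frequent than they were among those exposed.

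The same membership could affect other summaries. If the Safety population is used for them, an undosed subject's demographics (SAP section 9.2), Day -1 laboratory values (SAP section 9.4.3) and Day 1 predose vital signs and ECG (SAP sections 9.4.5 and 9.4.6) would enter the demographic and baseline summaries of a treatment that the subject did not receive.

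**Working it through.** **Planned numbers (SAP sections 5 and 7).**
- Total: 10 + 5 × 8 = 50, which reproduces the plan's approximate 50.
- LY3074828: 8 in Cohort 1 plus 5 × 6 in Cohorts 2 to 6 = 38.
- Placebo: 5 × 2 = 10 IV and 2 SC, together 12. Check: 38 + 12 = 50.

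**Where a randomized, undosed subject falls.**
- Safety population: in, because assigned to a treatment.
- Pharmacokinetic population: out, because no dose.
- TEAE numerator: out, because nothing can be postdose.
- TEAE denominator: in, if the table uses the Safety population. This step is inferred from SAP section 9.1.

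**Formula.** With k subjects with a TEAE, d dosed and u undosed in a column, the dosed-only percentage is 100 × k/d and the percentage as written is 100 × k/(d + u). For any u of zero or more, the second cannot exceed the first.

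**Assumptions.** The documents give no number of undosed subjects and no event counts. I take u = 1 and k = 1. For planned column size n, if the undosed subject is replaced, d = n, so the comparison is 1/n with 1/(n + 1). If not replaced, d = n − 1, so it is 1/(n − 1) with 1/n. Percentages are whole numbers, as in SAP section 13.1, with halves rounded up. Each entry reads dosed only → as written.

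| Column | n | Replaced | Not replaced |
|---|---|---|---|
| SC placebo | 2 | 1/2 = 50% → 1/3 = 33% | 1/1 = 100% → 1/2 = 50% |
| One race, active, Cohorts 2 to 6 | 3 | 1/3 = 33% → 1/4 = 25% | 1/2 = 50% → 1/3 = 33% |
| Japanese, active, Cohort 1 | 5 | 1/5 = 20% → 1/6 = 17% | 1/4 = 25% → 1/5 = 20% |
| Active arm, Cohorts 2 to 6 | 6 | 1/6 = 17% → 1/7 = 14% | 1/5 = 20% → 1/6 = 17% |
| Active arm, Cohort 1 | 8 | 1/8 = 13% → 1/9 = 11% | 1/7 = 14% → 1/8 = 13% |
| Pooled LY3074828 | 38 | 1/38 = 3% → 1/39 = 3% | 1/37 = 3% → 1/38 = 3% |

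With k = 3 in a six-subject active arm and a replacement, 3/6 = 50.0% becomes 3/7 = 42.9%; in pooled LY3074828, 3/38 = 7.9% becomes 3/39 = 7.7%.

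**Placebo columns.** SAP section 9.1 builds the IV placebo group from those who got it: "Data from subjects receiving placebo in the IV cohorts will be pooled to form 1 placebo group". Its wording already requires receipt, so I do not quantify it. SAP section 6 also lists a Pooled Placebo column without defining it. If that means IV plus SC (n = 12, an assumption) and the undosed subject was assigned SC placebo, 1/12 = 8% becomes 1/13 = 8% with replacement, and 1/11 = 9% becomes 1/12 = 8% without.

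**Other summaries.** A baseline or demographic mean that includes one extra subject moves up or down according to that subject's value. No direction can be given.

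**The case against.** The strongest reply is that two things must both happen, and the documents show neither: a subject is randomized and not dosed, and the TEAE tables take every member of the Safety population as denominator. SAP section 9.1 says only that summaries are generally restricted in this way, and denominators may be set in table shells that are not available. The window is also short: subjects are resident from Day -2 and are dosed on the morning of Day 1 (protocol section 7.1). All of this stands as a limit on likelihood. It does not remove the stated definition, which includes a subject that SAP section 7 expects might occur.

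A second reply is that SAP section 8 has every protocol deviation weighed when populations are assigned. This has force for subjects enrolled in error, since protocol section 8.1 treats departures from enrolment criteria as deviations. But the clause is discretionary and gives no rule for an undosed subject, and a subject who withdraws before dosing need not have deviated at all.

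A third concerns timing. Protocol section 9.3 describes Cohort 5 and the lower dose levels as already dosed, and the SAP was approved on 03-May-2018. For Cohorts 1 to 5 the unblinded sponsor could therefore have known whether anyone was undosed, and only Cohort 6 was clearly prospective in the amended protocol. The SC placebo row, with the largest shifts above, belongs to a cohort apparently already dosed. This stands and lowers the practical weight.

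Finally, event counts and counts of affected subjects are printed beside the percentage, all AEs are listed, and no inferential safety analysis is planned (SAP section 9.4.8). In columns this small, a careful reader will use the counts. That also stands.

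**Conclusion.** The definition, read with the protocol's meaning of enrolment, includes randomized but undosed subjects; confidence in that is high. That such a subject would reach the TEAE denominators is a natural inference, held with moderate confidence. Under the assumption of one undosed subject and one subject with a TEAE, the shift is 8 points in a three-subject race cell and 2 to 3 points in a six- or eight-subject active arm if the subject is replaced, and none after rounding in pooled LY3074828. It is zero if all randomized subjects are dosed. Severity: minor.

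Three stronger readings are not supported. A reader might infer that the trial's TEAE percentages are in fact understated; no passage shows that an undosed subject occurred. A reader might infer that only percentages are at risk; demographic and baseline summaries could be touched as well, if they use the Safety population. And a reader might infer that a dosing condition can only raise reported figures; that holds for TEAE percentages, while other summaries may move either way.

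**What to change.** In SAP section 8, define the Safety population as all randomized subjects who received any amount of study drug, LY3074828 or placebo. Show randomized but undosed subjects in disposition and listings only. Record the change in SAP section 11, which now reports no changes from the protocol. No protocol amendment is needed, because SAP section 3 lets the SAP supersede the protocol's statistical considerations provided that substantial differences are identified.

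Adding that subjects are analysed by the treatment they actually received, to match the Pharmacokinetic population, is an optional consistency edit. It changes nothing unless someone receives a treatment other than the one assigned.

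The cost is one sentence and one entry, plus a check that the table shells use the same denominator.
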